10. Urine collection intervals (for PK of BI 1291583, and [¹⁴C] -radioactivity assessment and metabolic profiling; planned time): On Day -1 or Day 1 (within 14 hours prior to dosing) pre-dose (blank) spot sample, on Day 1 prior to start of urine collection voiding of the bladder, 0-4, 4-8, 8-12, 12-24, 24-48, 48-72, 72-96, 96-120, 120-144, 144-168, 168-192, 192-216, 216 -240, 240-264, 264-288, 288-312, 312-336 hours after administration of BI 1291583 (C14). Thereafter, if warranted, 24 h collections are to be performed every 7 days starting on Day 21. Urine sampling for PK/[¹⁴C]-radioactivity and metabolic profiling will be stopped when release criteria for radioactivity recovery (see Section [3.1](#)) have been met (earliest stopping on Day 15). “+” means: end of last collection interval, start of following collection interval. For details on sample usage see Section [5.3.2.2](#).
[REDACTED]

11. All stools ([¹⁴C]-radioactivity and metabolic profiling) will be collected quantitatively in portions up to 336 hours (sampling intervals of 0-24, 24-48, 48-72, 72-96, 96-120, 120-144, 144-168, 168-192, 192-216, 216 -240, 240-264, 264-288, 288-312, 312-336 hours after administration of BI 1291583 (C14). Thereafter, if warranted, 24 h collections are to be performed every 7 days starting on Day 20. Further details regarding home collection see footnote 13. For blank sample see footnote 14. Faeces sampling for [¹⁴C]-radioactivity and metabolic profiling will be stopped when release criteria for radioactivity recovery (see Section [3.1](#)) have been met (earliest stopping on Day 15). “+” means: end of last collection interval, start of following collection interval. For details on sample usage see Section [5.3.2.3](#)).
[REDACTED]

12. The planned times for admission, discharge, start and end of the urine and faeces collection intervals are approximate. The procedures are to be performed within a time window of \pm 4 hours to the planned time. However, the ambulatory onsite collections should be at least over 24 hours.

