13. Subjects are to collect faeces at home within 24 h intervals before admission to once-weekly in-house collection intervals. Home collection intervals: Day 20-21, 27-28, 34-35, and 41-42. If faeces are collected in the subsequent in-house collection interval, faeces collected at home will be discarded. If no faeces is collected in the subsequent in-house collection interval (no defecation), last faeces collected at home in the 24 h interval before admission be used instead for analysis.

14. Subjects will collect a pre-dose (blank) faeces sample at home or at the site on Days -2 (after screening, if screening is on Day -2), -1 or 1 (prior to dosing) in specific containers provided by [REDACTED]. Only the last pre-dose faeces sample will be analysed (if applicable).

15. Subjects are to be fasted for at least 10 h before drug administration.

16. Prior to discharge from trial site on Day 15 confirmation of fitness will be performed including physical examination, ECG, vital signs, safety laboratory, recording of AEs and concomitant medication.

17. Testing for SARS-CoV-2 (PCR or antigen test) will be performed on Day -1 prior to admission, on Day 2, and at each admission to the trial site for 24-hours visits. Additional tests may be performed as needed based on the current status of the pandemic.

18. [REDACTED]

19. Formal assessment and confirmation of fitness is based on questioning for adverse events and concomitant medication and personal judgement of the investigator.

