3. DESCRIPTION OF DESIGN AND TRIAL POPULATION

3.1 OVERALL TRIAL DESIGN

The trial will be performed as an open-label, single-arm, single-dose trial in healthy male subjects to investigate the basic pharmacokinetics of BI 1291583, its metabolites (M407[1] / BI 1373234, M396(1) / CD 18507, M397(1) / CD 17849, M549(1) / CD 16785 and M141(1) / CD 16426) and [¹⁴C]-radioactivity, including mass balance, excretion pathways and metabolism following a single oral dose of [REDACTED] BI 1291583 (C-14).

A total of 8 healthy male subjects are planned to participate in the trial.

The planned radioactive dose per subject is approximately ≈ 0.36 MBq (0.04 mSv).

On Day 1, subjects will receive the drug product, i.e. [REDACTED] BI 1291583 (C-14) and will then stay in the study centre up to the morning of Day 15 for collection of samples of blood, urine and faeces, and if applicable for collection of vomit (within 24 hours after drug administration).

[REDACTED]

Subjects will be readmitted to the study centre for 24 h collection intervals of urine and faeces on Days 21, 28, 35, and 42, if release criteria have not been met before. Within 24 hours before each of these once-weekly in-house collection intervals, subjects are to collect faeces at home. This 24-h interval home collection faeces will be used for analysis in case no defecation occurs in the subsequent 24 h in-house collection interval. Otherwise it will be discarded.

For determination of whether release criteria have been reached for individual subjects, [¹⁴C]-radioactivity will be measured in excreta (urine, faeces), and vomit, if applicable. The actual recovery results will be reported as a percentage of the administered dose.

If the following release criteria have been met, the subsequent 24 h collection intervals after Day 15 will not be performed:

- Greater than or equal to 90% of the administered [¹⁴C] dose has been recovered in urine and faeces combined over the investigational period

and

- If <1% of the [¹⁴C] dose administered has been collected in urine and faeces within 2 separate, consecutive 24-h intervals

Note:

For calculation of release criteria during clinical conduct the fraction of administered [¹⁴C] dose will be rather underestimated as it will be based on the available samples, only. For the final analysis, the total excreted [¹⁴C]-radioactivity will be derived including an interpolation method to account for the time periods without samples taken (see Section [7.2.2](#)).

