In this trial the term “release” does not mean that no further assessments are required and that the end of study examination can be performed. Subjects need to return for blood sampling

Proprietary confidential information © 2023 Boehringer Ingelheim International GmbH or one or more of its affiliated companies

(PK and metabolite profiling) even if formal release criteria for the excretion of ¹⁴C-labeled drug material in excreta have been met.

If a subject is unable to attend one of the ambulatory visits, they may be allowed to reschedule the visit if needed. Irrespective of whether release criteria have been met or not, no further collections are planned after collection interval day 42-43.

[figure not shown]
An overview of all relevant trial activities is provided in the [Flow Chart](#). For visit schedule and details of trial procedures at selected visits, refer to Sections [6.1](#) and [6.2](#), respectively.

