5.3.2.3 Sampling of faeces

Faeces will be collected at time points or in intervals as indicated in the [Flow Chart](#):

- To determine total [¹⁴C]-radioactivity
- To investigate the metabolic profiling of BI 1291583 (to be reported separately)

A blank sample will be taken within approximately 48 hours prior to drug administration. If several samples are available, the sample closest to drug administration will be used for analyses.

Faeces samples collected after administration of BI 1291583 (C-14) until release criteria are met are planned to be used for determination of [¹⁴C]-radioactivity. Samples to be used for metabolic profiling will be selected according to the levels of radioactivity in each faeces sample interval. For faeces samples to be discarded (see footnote 13 and 14).

All stools will be collected continuously in portions up to 336 hours after drug administration. All stool portions will be taken quantitatively at the time-points depicted in the [Flow Chart](#). The weight of the faeces and the exact times of faeces collection will be recorded in the eCRF.

If subjects are to collect faeces during the ambulatory phase of the study (see Section [3.1](#) for release criteria), subjects are to collect faeces at home within 24 h intervals before admission to once-weekly in-house collection intervals. Home collection intervals are (if applicable): Days 20-21, 27-28, 34-35, and 41-42. All faeces samples (including home collection, if

Proprietary confidential information © 2023 Boehringer Ingelheim International GmbH or one or more of its affiliated companies

applicable) will be shipped [REDACTED]. If faeces is collected during in-house collection interval, this faeces sample will be used for analysis and the respective home collection faeces sample has to be discarded. If no faeces is collected in the subsequent in-house collection interval (no defecation), faeces collected at home will be used instead for analysis.

[figure not shown]
For a detailed description of faeces sample preparation, sample storage, labelling, and sample shipment refer to the laboratory manual.

[figure not shown]

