6.2.2 Treatment period

Each subject is expected to participate in one treatment period (Visit 2).

Proprietary confidential information © 2023 Boehringer Ingelheim International GmbH or one or more of its affiliated companies

On Day -1 of the treatment period study participants will be admitted to the trial site and kept under close medical surveillance until discharge from the trial site on Day 15. In the morning of Day 15, the subjects will then be allowed to leave the trial site after formal assessment and confirmation of their fitness.

Until release criteria (see Section [3.1](#)) have been reached, subjects will take part in the 24-h collection intervals of urine and faeces. For these additional 24 h collection intervals, subjects will be admitted to the trial site on Days 21, 28, 35, and 42. One day later, on Days 22, 29, 36, and 43, respectively, subjects will be discharged from the trial site after formal assessment and confirmation of their fitness.

Within 24 h before each once-weekly in-house collection interval, subjects are to collect faeces at home (beginning of home collections on Days 20, 27, 34, and 41). Faeces collected in these 24 h home-collection intervals will be used for analysis in case no defecation occurs in the subsequent 24 h in-house collection interval. E.g., if no defecation occurs in in-house collection interval Day 21-22, faeces of home-collection interval Day 20-21 will be used for analysis. If, however, faeces are collected in the subsequent 24 h in-house collection interval, faeces collected at home will be discarded. Once release criteria are reached, home collections will be stopped.

Irrespective of whether release criteria have been met or not after collection interval Days 42-43, no further collections are planned. For details on time points and procedures for collection of plasma, whole blood, urine and faeces samples for PK analysis and mass balance assessment, refer to [Flow Chart](#) and Section [5.3.2](#).

The safety measurements performed during the treatment period are specified in Section [5.2](#) of this protocol and in the [Flow Chart](#). AEs and concomitant therapy will be assessed continuously from obtaining subject's written informed consent until the end of trial examination. For details on times of all other trial procedures, refer to the [Flow Chart](#).

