7.2.2 Primary endpoint analyses

The primary endpoints (refer to Section [2.1.2](#)) will be calculated according to the relevant BI internal procedures. The analysis will be descriptive in nature. To avoid underestimation of the total recovery of [¹⁴C], the excretion during the non-sampling phase of the study will be estimated using linear interpolation between the observed 24-h sampling periods before and after the non-sampling period for urine and feces respectively.

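### Release clause 2 can be met on Day 15 because no stool was passed on the last two in-house days, not because excretion has ended

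*Protocol*

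**What the plan says.** Protocol Section 3.1 and the release criteria under the Flow Chart set two conditions in the same words. Clause 1 asks for at least 90% of the dose in urine and faeces combined. Clause 2 asks that less than 1% of the [14C] "dose administered has been collected in urine and faeces within 2 separate, consecutive 24-h intervals". The earliest stopping point is Day 15 (Flow Chart footnotes 10 and 11). The Note in Section 3.1 says that, during conduct, the fraction of administered [14C] "dose will be rather underestimated as it will be based on the available samples, only".

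For the weekly visits the protocol does deal with a missing stool. Flow Chart footnote 13 reads: "If no faeces is collected in the subsequent in-house collection interval (no defecation), last faeces collected at home" in the preceding 24 h is analysed in its place. Section 5.3.2.3 repeats this ("faeces collected at home will be used instead for analysis"), as do Sections 3.1 and 6.2.2. No matching rule exists for the daily intervals up to 336 h.

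After release, Section 6.2.2 says: "Once release criteria are reached, home collections will be stopped". Section 3.1 keeps the blood visits ("Subjects need to return for blood sampling") but not the excreta collections. Section 7.2.2, repeated in SAP Section 7.4.1, fills unsampled time "using linear interpolation between the observed 24-h sampling periods before and after the non-sampling period". The SAP adds nothing on release.

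**The concern.** Clause 2 is meant to show that excretion has tailed off, but it tests what was collected. On a day without a stool, faecal radioactivity stays in the gut and the interval scores urine only. Two such days at the end of the in-house stay look the same as finished excretion. The protocol avoids this reading at the weekly visits, but not on the days that decide release on Day 15.

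The Note in Section 3.1 presents the use of available samples as cautious. That is true for clause 1, where a retained stool makes 90% harder to reach. For clause 2 it works the other way, since a retained stool makes the 1% limit easier to meet.

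The clause also does not say that the two intervals must be the latest ones. Read literally, any earlier pair of low days would do.

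At stake are the primary endpoints of individual subjects. After release there is no later excreta sample, so the interpolation has no second anchor and adds nothing.

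**Working it through.** **Inputs from the documents.** The 90% and 1% limits; 24-h intervals; daily collection to 336 h; weekly collections starting at 485 h and ending at 509, 677, 845 and 1013 h; 8 subjects. The plan states no figure for this rule, so there is none to reproduce.

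**Assumptions (not in the documents).** Mono-exponential excretion with the whole dose eventually excreted; half-life H of 3, 3.25 or 3.5 d; urine share u of 20% or 40%; a stool on each day with probability p of 0.7 or 0.8, independently; faecal radioactivity held until the next stool. This gives 12 settings.

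**Step 1: one subject.** Cumulative excretion is R(t) = 100 × (1 − 0.5^(t/H)). Take u = 20%, a stool every day up to 288 h (12 d), then none to 336 h (14 d). Recovery is 0.8 × R(12) + 0.2 × R(14).

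| H (d) | Faeces to 288 h | Urine to 336 h | Recovered | Last two intervals (urine only) | Day 15 |
|---|---|---|---|---|---|
| 3 | 0.8 × 93.75 = 75.0 | 0.2 × 96.06 = 19.2 | 94.2% | 0.26%, 0.20% | released, 5.8% outstanding |
| 3.5 | 0.8 × 90.71 = 72.6 | 0.2 × 93.75 = 18.75 | 91.3% | 0.33%, 0.27% | released, 8.7% outstanding |
| 4 | 0.8 × 87.5 = 70.0 | 0.2 × 91.16 = 18.2 | 88.2% | 0.40%, 0.33% | kept (clause 1) |

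With a stool every day, the last two intervals hold 1.29% and 1.02% at H = 3 d, and 1.67% and 1.37% at H = 3.5 d. Each is at least 1%, so the subject is kept. Excretion is the same and the decision is opposite.

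**Step 2: how often.** All 2^14 in-house stool patterns were enumerated, with release if recovery is at least 90% and each of the last two intervals is below 1%. Over the 12 settings, 3.2–8.9% of subjects are released on Day 15, every one through two stool-free final days, with a mean of 5.6–8.7% of dose outstanding. The upper bound on the rate is (1 − p)²: 0.3² = 9% and 0.2² = 4%.

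**Step 3: effect on the endpoint.** Averaged over all subjects, the outstanding dose is 0.2–0.7 points. For a released subject, the faecal shortfall against the true value at the end of the Day 28–29 collection (677 h, 28.2 d) is 3.9–7.1 points. One such subject moves a mean of 8 by 3.9/8 = 0.5 to 7.1/8 = 0.9 points. The chance that none of 8 is affected is between (1 − 0.089)^8 = 47% and (1 − 0.032)^8 = 77%.

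**Step 4: limits.**
- H = 4 d: nobody is released.
- p = 0.9: about 1% of subjects.
- H = 2 d: 87–96% are released on Day 15, but only 0.8% of dose remains.
- Fast-plus-slow profile (80% at 1.5 d, 20% at 10 d): two empty days add only about 1 point.

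**Step 5: any two consecutive intervals.** If an earlier pair may count, release on Day 15 rises to 10–37% at H = 3–3.5 d, and to 3–23% at H = 4 d.

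**The case against.** The strongest reply is that this is a small effect built on assumptions. The release rate largely restates the assumed stool frequency, since it cannot exceed (1 − p)². The effect also sits in a narrow half-life band. Section 3.2 bases the sampling duration on rat excretion data and clinical pharmacokinetics, which the sponsor has and the public text does not show. The trial is descriptive and has no recovery threshold to pass. The endpoint runs to the last quantifiable time point over 2 to 6 weeks, so the Day 29 comparison is a yardstick chosen here, not one in the plan. Any rule of this type accepts some unexcreted dose. The laboratory manual and internal procedures were not available and may settle the scoring. All of this stands, and it limits the size of the point. It does not change the fact that the protocol's rule can release a subject because no stool was passed.

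Three stronger readings are tempting, and the documents do not support them:

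- **Stool-free weekly in-house intervals are unscored.** They are covered by the home-collected stool. Only a week with no stool in either place is left open.
- **Summing the two intervals changes everything.** A summed reading would change release rates sharply (at H = 2.5 d, 4–9% instead of 58–68%). But the clause calls the intervals separate and, unlike clause 1, does not say combined, so the per-interval reading is the natural one.
- **The mass balance is at risk.** Clause 1 limits what can be missing at release to 10% of dose.

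**Conclusion.** The point holds as a minor design weakness. Clause 2 counts collected radioactivity, does not fix the two intervals as the most recent, and gives a stool-free daily interval 0% for faeces. Two such days at the end of the in-house stay can therefore release a subject on Day 15 with excretion still under way.

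Under the assumed half-life of 3–3.5 d and daily stool probability of 0.7–0.8, this affects about 3–9% of subjects, each with 5.6–8.7% of dose outstanding. The expected effect on the group mean is below about 0.7 points; an affected subject's own value would be visibly low. That the mechanism exists follows from the text. How often it operates rests wholly on the assumptions, and the sponsor's own excretion and pharmacokinetic data should replace them.

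**What to change.** Reword clause 2 in Section 3.1 and in the Flow Chart to: *<1% of the dose in each of the two most recent 24-h collection intervals, at least one of which includes a stool (weekly phase: using the home-collected stool where applicable).* A subject with two stool-free final in-house days then goes on to the Day 21 collection, which is already scheduled.

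**Effect and cost.** No subject is released early in the 12 settings. The cost is an extra 24-h stay for subjects with two stool-free final days, about 4–9% under the assumed stool frequencies. The retained blood visits do not replace that stay. At H = 2 d, release on Day 15 falls only from 87–96% to 78–92%.

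**What not to add.** Requiring a stool in both intervals would cut release at H = 2 d to 45–61% for no real gain. The interpolation start value should also stay as planned. Starting from the last interval with a stool gives an average of 1.17–1.48% of dose per day against a true 0.82% (H = 3 d, u = 20%); the plan's rule gives 0.88–0.92%.

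**Limit of the fix.** A stool passed between discharge and the next collection is still lost. In the H = 3 d example, keeping the subject to Day 29 under the planned interpolation raises faecal recovery only from 75.0% to 76.2%, against a true 79.9%. The rewording makes the release decision sound and keeps later excretion under observation; it does not restore that subject's full value.

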3.2 DISCUSSION OF TRIAL DESIGN, INCLUDING THE CHOICE OF CONTROL GROUP

This is a well-known design for a [¹⁴C] human study for investigation of absorption, metabolism, and excretion including determination of mass balance. Inclusion of a control group is not required for this investigation. The study will use a low amount of [¹⁴C]-radioactivity and accelerator mass spectrometry (AMS) for the measurement of [¹⁴C] for sensitive detection, tracking and quantification of the parent drug and metabolites of mass balance.

Based on excretion data of drug-related radioactivity in the rat ADME trial [[n00256437](#), [n00258671](#)] and the available PK data from clinical trials (see Section [1.2.1.2](#)) a prolonged sampling duration was planned.

Following 15 days in-house excreta collection after dosing, subjects will return on a weekly basis **for in-house 24-h collection intervals (urine/faeces)** for up to 6 weeks (i.e., up to Day 43) after dosing **as long as release criteria are not met** (Section [3.1](#)).

Blinding and randomisation is not necessary because all subjects receive the same treatment. Furthermore, the main endpoints cannot be subjectively influenced as they are determined in urine, faecal and blood samples.

3.3 SELECTION OF TRIAL POPULATION

It is planned that 8 healthy male subjects will enter the trial. A sample size of 6 evaluable subjects is generally considered adequate for a human ADME study [[R22-3641](#)]. They will be recruited from the volunteers' pool of the trial site or recruited via e.g. external databases and advertisements.

Healthy male subjects are an appropriate population for the objectives of this trial, since they provide relatively stable physiological, biochemical and hormonal conditions, i.e. the absence of disease-related variations and relevant concomitant medications.

A log of all subjects enrolled into the trial (i.e. who have signed informed consent) will be maintained in the ISF, irrespective of whether they have been treated with investigational drug or not.

3.3.1 Main diagnosis for trial entry

The trial will be performed in healthy subjects.

Please refer to Section [8.3.1](#) (Source Documents) for the documentation requirements pertaining to the in- and exclusion criteria.

3.3.2 Inclusion criteria

Subjects will only be included in the trial if they meet the following criteria:

1. Healthy male subjects according to the assessment of the investigator, as based on a complete medical history including a physical examination, vital signs (BP, PR), 12-lead ECG, and clinical laboratory tests
2. Age of 18 to 55 years (inclusive)
3. BMI of 18.5 to 29.9 kg/m² (inclusive)
4. Signed and dated written informed consent in accordance with ICH-GCP and local legislation prior to admission to the trial

[figure not shown]
3.3.3 Exclusion criteria

[figure not shown]
Subjects will not be allowed to participate, if any of the following general criteria apply:

1. Any finding in the medical examination (including BP, PR or ECG) deviating from normal and assessed as clinically relevant by the investigator
2. Repeated measurement of systolic blood pressure outside the range of 90 to 140 mmHg, diastolic blood pressure outside the range of 50 to 90 mmHg, or pulse rate outside the range of 45 to 90 bpm
3. Any laboratory value outside the reference range that the investigator considers to be of clinical relevance
4. Any evidence of a concomitant disease assessed as clinically relevant by the investigator
5. Gastrointestinal, hepatic, renal, respiratory, cardiovascular, metabolic, immunological or hormonal disorders
6. Cholecystectomy or other surgery of the gastrointestinal tract that could interfere with the pharmacokinetics of the trial medication (except appendectomy or simple hernia repair)
7. Diseases of the central nervous system (including but not limited to any kind of seizures or stroke), and other relevant neurological or psychiatric disorders
8. History of relevant orthostatic hypotension, fainting spells, or blackouts
9. Relevant chronic or acute infections
10. Any documented active or suspected malignancy or history of malignancy within 5 years prior to screening, except appropriately treated basal cell carcinoma of the skin
11. History of relevant allergy or hypersensitivity (including allergy to the trial medication or its excipients)

Proprietary confidential information © 2023 Boehringer Ingelheim International GmbH or one or more of its affiliated companies

12. Use of drugs within 14 days (or 5 half-lives, whichever is longer) of planned administration of trial medication that might reasonably influence the results of the trial (including drugs that cause QT/QTc interval prolongation)
13. Intake of an investigational drug in another clinical trial within 30 days of planned administration of investigational drug in the current trial, or concurrent participation in another clinical trial in which investigational drug is administered.
14. Smoker (more than 5 cigarettes or 1 cigar or 1 pipe per day)
15. Inability to refrain from smoking during in-house confinement
16. Alcohol abuse (average intake of more than 21 units per week)
17. Drug abuse or positive drug screening
18. Blood donation of more than 100 mL within 30 days of planned administration of trial medication or intended blood donation during the trial
19. Intention to perform excessive physical activities within 5 days prior to the administration of trial medication or during the trial
20. Inability to comply with the dietary regimen of the trial site
21. A marked prolongation of QT/QTc interval (such as QTc intervals that are repeatedly greater than 450 ms) or any other relevant ECG finding at screening
22. A history of additional risk factors for *Torsade de Pointes* (such as heart failure, hypokalaemia, or family history of Long QT Syndrome)
23. Subject is assessed as unsuitable for inclusion by the investigator, for instance, because the subject is not considered able to understand and comply with study requirements, or has a condition that would not allow safe participation in the study.

For restrictions of the trial, refer to Section [4.2.2](#).

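### No visible eligibility criterion addresses bowel habit, although after Day 15 the interpolated part of fe_faeces,0-tz relies on a stool falling in a weekly window and standing for one day's output

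*Protocol*

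**What the plan says.** - **Eligibility.** Criterion 5 of Protocol 3.3.3 excludes "Gastrointestinal, hepatic, renal, respiratory, cardiovascular, metabolic, immunological or hormonal disorders", and criterion 6 excludes relevant gastrointestinal surgery. Criterion 23 lets the investigator exclude an unsuitable subject, for example where "the subject is not considered able to understand and comply with study requirements". None of the 4 inclusion and 23 exclusion criteria mentions stool frequency.
- **To Day 15.** Protocol 5.3.2.3: "All stools will be collected continuously in portions up to 336 hours after drug administration".
- **After Day 15, if release criteria are not met.** Protocol 3.1: "Subjects will be readmitted to the study centre for 24 h collection intervals of urine and faeces on Days 21, 28, 35, and 42". Flow Chart footnote 13 adds a back-up: "Subjects are to collect faeces at home within 24 h intervals before admission to once-weekly in-house collection intervals". Protocol 5.3.2.3 gives the substitution rule: "If no faeces is collected in the subsequent in-house collection interval (no defecation), faeces collected at home will be used instead for analysis". If a stool is passed in-house, the home sample is discarded.
- **Analysis.** Protocol 7.2.2, repeated in TSAP 7.4.1, fills the unsampled time by "linear interpolation between the observed 24-h sampling periods before and after the non-sampling period", separately for urine and faeces.
- **Size.** Protocol 7.5 enters 8 subjects to obtain at least 6 evaluable, without a power calculation.

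**The concern.** fe_faeces,0-tz is one of the two primary endpoints. After Day 15 the gap-filling step works well only if each analysed window holds about one day's faecal output. The protocol foresees in-house days without defecation and provides a home substitute, but nothing visible selects for subjects in whom such days are rare. Criterion 5 does not do so, because passing stool every 2 or 3 days is not a disorder. The examples in criterion 23 are comprehension, compliance and safety, so they do not prompt the question.

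The late phase is not a remote case. Protocol 3.2 says that prolonged sampling was planned on the basis of rat excretion data and clinical PK data. With at most 8 values, one subject with a large interpolation error is noticeable in the mean and SD.

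**Working it through.** The plan gives no figure for this point, so there is none to reproduce. The check uses the Flow Chart times and states the assumptions that the documents do not supply.

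**1. How much is interpolated.** In-house windows start at 485, 653, 821 and 989 h and each lasts 24 h. The gaps are 485 − 336 = 149 h, then 653 − 509 = 821 − 677 = 989 − 845 = 144 h. Of the 1013 − 336 = 677 h after Day 15, 4 × 24 = 96 h are sampled and 149 + 3 × 144 = 581 h are interpolated.

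**2. Weight of one window.** Each gap contributes (gap/24) × the mean of the two flanking 24-h amounts. A middle window therefore counts 1 + 144/24 = 7 times. The 312–336 h interval is also an anchor, with weight 149/48 = 3.1 on top of its own measured content, and it has no home substitute.

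**3. Direction of the error.** Take a perfectly regular habit of one stool every D days (D ≥ 1) and ignore decline over time. An in-house window alone catches a stool with probability 1/D, and that stool holds D days of output. The expected content is one day's output: noisy but unbiased. With the home back-up the probability of a catch is min(1, 2/D), so the expected content is min(D, 2) days, still counted as one. At D = 2 or 3 the weekly anchors are overstated about twofold.

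**4. Simulation.** Assumptions from outside the documents:
- Cumulative gut input F(1 − exp(−k(t − 12 h))), with F = 70% of dose and k = ln 2 / half-life.
- Gamma stool intervals (shape 6) with mean 1, 2 or 3 days.
- Follow-up to Day 43.
- A week with home and in-house windows both empty counts as zero, since no rule is visible.

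The plan's collection, substitution and interpolation rules are applied. Error is the estimate minus the amount truly passed by 1013 h. SD of the per-subject error, in points of dose:

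| Half-life | 1 stool/day | 1 per 2 days | 1 per 3 days |
|---|---|---|---|
| 48 h | 0.8 | 2 | 4 |
| 80 h | 2.7 | 6 | 10 |
| 120 h | 4.6 | 10.6 | 17.5 |
| 168 h | 6 | 14 | 23 |

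At 120 h the mean error is +2.5, +7.3 and +9.7 points. The in-house window is empty in 16%, 52% and 67% of weeks, and both windows are empty in 0.4%, 16% and 37%.

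**5. What is measured directly.** With one stool every 3 days, the share of the Day-43 faecal total already collected by 336 h is about 98% at 48 h, 91% at 80 h, 80% at 120 h and 70% at 168 h. For a subject who stops at Day 15, the only loss is material still in the gut: about 0.9, 2.0 and 3.2 points at 120 h for one stool every 1, 2 and 3 days.

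**6. Effect on the group mean.** One subject with an error of 17.5 points moves a mean of 8 by 17.5/8 = 2.2 points, and a mean of 6 by 17.5/6 = 2.9.

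**The case against.** A reader might infer that such a subject's fe_faeces is almost uninformative. The documents do not support that. Collection to 336 h is continuous and quantitative, so infrequent stools shift radioactivity between intervals but lose none already passed. Most of the total is measured directly over the assumed range, and the home back-up lowers the chance of an empty week.

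The stronger objection is that the problem lies in the analysis rules rather than in enrolment. Much of it does. Averaging the home and in-house days over 48 h, and anchoring on the last four in-house days, cuts the SD at 120 h from about 10.5 to 5.1 (one stool per 2 days) and from 17.4 to 8.5 (one per 3 days). The mean error falls to about +3 in both. Scaling each stool by the time since the previous one gives SDs of 1.9, 4.2 and 8.0 for one stool every 1, 2 and 3 days and removes nearly all bias. Treating empty pairs as missing gives 4.2, 11.1 and 29.4. So a better rule removes roughly half the SD or more, but in each of these comparisons the infrequent defaecator remains noisier. Enrolment still matters.

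Other points that stand:
- Half-life, faecal share and stool habit are assumptions. At 48 h the effect is small, and such a subject might well be released at Day 15: 1 − 2^(−324/48) = 99% of faecal input has occurred by then.
- The documents give no basis for how many of 8 men would be infrequent defaecators.
- The analysis is descriptive, with medians, quartiles and individual listings, so an outlying subject would be visible.
- Criterion 23 and the replacement rule in Protocol 3.3.5 give some room to act.
- Missing figures next to the criteria lists mean that a hidden criterion cannot be ruled out, although the numbering 1 to 23 is unbroken.
- A rule for empty windows may exist in the sponsor's internal procedures, to which Protocol 7.3.2 and TSAP 6.6 refer.

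**Conclusion.** The point holds as a cheap improvement to eligibility. No visible criterion addresses bowel habit. For subjects not released at Day 15, the interpolated part of a primary endpoint is less precise and biased upward if they defaecate infrequently and excrete slowly. Both conditions are needed. Under the stated assumptions the error SD for one stool every 3 days ranges from about 4 points at a 48 h half-life to about 23 at 168 h, against 0.8 to 6 with daily stools. The figures depend on counting empty window pairs as zero and on follow-up to Day 43. They describe individual subjects; the group-level effect depends on how many such men enrol, which cannot be derived from the documents.

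**What to change.** Add to Protocol 3.3.3 an exclusion for an irregular defecation pattern by history: usually fewer than one stool per 2 days, or recurrent constipation or diarrhoea. Ask at screening and reconfirm on Day -1. The cost is one criterion, one question and some extra screen failures, with no added procedure.

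This threshold removes the worst case but still admits men with one stool every 2 days (SD about 10.6 at 120 h). A stricter one-per-day threshold would bar more healthy volunteers. The criterion should therefore go together with a rule in Protocol 7.2.2 and TSAP 7.4.1 that states how a week with both windows empty is handled, and how a stool holding more than one day of excretion enters the interpolation.
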